#### **B. Description of Population to be Enrolled:**

The subject population will consist of a convenient sample of people. The subjects will have various ethnicity, age, and gender. An estimated total of 30 subjects will be enrolled. The subjects must be normal intact individuals and/or persons with amputation who are able to understand and follow directions in English, assessed by their ability to respond during the recruitment and consent process. Exclusion criteria include any subjects that are not able to understand the procedures and/or are less than 18 years of age.

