## Statistical Power and Design

### Power calculation:

The primary outcome measure will be the improvement in intra-subject CAPPFUL scores while using the Point Digit system versus no prosthesis. CAPPFUL provides a full-scale score ranging from 0 to 100. The mean and standard deviation of CAPPFUL for partial hand amputees (n=17) is provided in [28] as  $71.37 \pm 10.15$ . If we consider a difference in CAPPFUL functional scores of one standard deviation (10.15) as clinically significant, a sample size of at least 11 subjects will be needed to reject the null hypothesis that the means are equal with power of 0.9 and a probability of Type I error of 0.05 (z-test for normally distributed data with known standard deviation). This sample size paired with the CAPPFUL metric will provide actionable evidence to support the Point Digit.

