### Data analysis:

Data will be gathered by Arm Dynamics and provided to the independent researchers at the Biomechatronics Development Laboratory. The data will be evaluated carefully by study team members without conflicts of interest to determine the distribution of all scores in the population studied and the variability of scores within and between uses of the two systems. We will measure the effectiveness of the *Point Digits* using the primary measures: CAPPFUL and WI. Both outcome measures will be studied over time by comparing the results across stage 0, 1, and 2. We hypothesize that the CAPPFUL and WI measures will increase from stage 0 to stage 2. Average scores across subjects will be studied using One-Factor ANOVAs to determine differences across the testing sessions. Post-hoc analysis (Tukey-Kramer post-hoc analysis) will be performed as necessary. One-sample t-tests will be used to compare the outcome measures with the existing dataset from Arm Dynamics. Pair-wised t-tests may be performed when a subject matches the demographic, functional, or psychological profiles of an existing subject within the dataset. Then, differences can be studied based on the prosthetic components, amputation level, or other subject attributes. A probability of Type I error of 0.05 will be used to determine statistical significance. Sex will not be a factor in this study.

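### The SAP tests an intra-subject primary outcome with One-Factor ANOVAs that name no subject term, and plans no same-subject paired test

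*SAP*

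**What the plan says.** The SAP's power calculation section sets a within-person outcome: "The primary outcome measure will be the improvement in intra-subject CAPPFUL scores while using the Point Digit system versus no prosthesis". It sizes the study for a 10.15-point difference, equal to the SD of CAPPFUL scores it cites, using a z-test with power 0.9 and alpha 0.05: "a sample size of at least 11 subjects will be needed to reject the null hypothesis that the means are equal".

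The SAP's data analysis section names two primary measures ("using the primary measures: CAPPFUL and WI") and follows them through three stages: "Both outcome measures will be studied over time by comparing the results across stage 0, 1, and 2". The test for this is: "Average scores across subjects will be studied using One-Factor ANOVAs to determine differences across the testing sessions". Then: "Post-hoc analysis (Tukey-Kramer post-hoc analysis) will be performed as necessary".

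Two other tests are named. One-sample t-tests compare the outcomes with the existing Arm Dynamics dataset. The paired tests are optional and use that same dataset: "Pair-wised t-tests may be performed when a subject matches the demographic, functional, or psychological profiles of an existing subject within the dataset".

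The protocol's data analysis plan (section IV.F) refers only to standard methods in MATLAB. On numbers, section IV.B says: "An estimated total of 30 subjects will be enrolled". That population may include people without amputation.

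**The concern.** The outcome is a change within a person, but the named test is the ordinary one-way ANOVA unless something more is said. That ANOVA treats the three stage scores as if they came from different people. The differences between people, which cancel out of a within-person change, then stay in the error term. With positively correlated scores the F-test rejects too rarely, both under the null and when the device works.

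Nothing else in the plan fills the gap. The one-sample tests look outward to an external dataset, the paired tests join two different people, and the z-test appears only in the sizing. At stake is the power of the primary analysis. The visible text also does not define the stages, so it is unclear which stage contrast is Point Digit versus no prosthesis.

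**Working it through.** **Inputs.** From the SAP: difference 10.15, SD 10.15, alpha 0.05, power 0.90, n = 11, three stages. Not given, so assumed: the within-person correlation rho (0 to 0.7), compound symmetry, stage 0 = no prosthesis, and the stage 1 mean.

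**1. The plan's own sample size.**
- One-sample (difference) z-test, two-sided: n = ((1.960 + 1.282) × 10.15/10.15)² = 10.51, rounded up to 11. This matches.
- One-sided: 8.56, giving 9.
- Two independent groups, two-sided: 2 × 10.51 = 21.01, giving 22 per group.

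Of these, only the two-sided one-sample form gives 11. With an intra-subject outcome, that means an SD of differences of 10.15. If 10.15 is also the SD of the scores, then 10.15 = 10.15 × √(2(1 − rho)), so rho = 0.5.

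**2. True Type I error of the One-Factor ANOVA (no subject term, nominal 0.05).** With three stages and compound symmetry,

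P(reject) = (1 + 2a)^−(n−1) × (1 + 2ac)^−((n−1)/2), where a = F(0.95; 2, 3(n−1)) / (3(n−1)) and c = (1 + 2rho)/(1 − rho).

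For n = 11, a = 3.316/30 = 0.1105.

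| rho | c | Type I error |
|---|---|---|
| 0 | 1 | 0.050 |
| 0.3 | 2.29 | 0.018 |
| 0.5 | 4 | 0.006 |
| 0.7 | 8 | 0.001 |

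**3. Power at n = 11, gain of 10.15 from stage 0 to stage 2.** Repeated-measures power uses the noncentral F on 2 and 20 df, with noncentrality n × (sum of squared stage deviations) / (score variance × (1 − rho)). In SD units a linear gain has stage means 0, 0.5 and 1 and a sum of squares of 0.5, so at rho = 0.5 the noncentrality is 11 × 0.5/0.5 = 11 and power is 0.79. One-factor power averages a noncentral chi-square tail over the distribution of the correlated error sum of squares. Direct simulation agrees (0.46 at rho = 0.5).

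| rho | Score SD 10.15: one-factor | Score SD 10.15: repeated measures | Difference SD 10.15: one-factor | Difference SD 10.15: repeated measures |
|---|---|---|---|---|
| 0 | 0.50 | 0.48 | 0.81 | 0.79 |
| 0.3 | 0.48 | 0.64 | 0.65 | 0.79 |
| 0.5 | 0.46 | 0.79 | 0.46 | 0.79 |
| 0.7 | 0.44 | 0.95 | 0.185 | 0.79 |

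In the last two columns the score SD is 10.15/√(2(1 − rho)) = 7.18, 8.58, 10.15 and 13.10.

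If the full gain is already present at stage 1 (rho = 0.5, score SD 10.15), power is 0.63 against 0.90. Tukey's comparison of stage 0 with stage 2 without a subject term does not rescue the plan: its power at rho = 0.5 is 0.46 for a linear gain, against 0.85 for a same-subject paired t-test.

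**4. Power with 30 analysed, linear gain.** One-factor power is 0.94 to 0.99 with score SD 10.15. With difference SD 10.15 it is 0.98 or more up to rho = 0.5, and 0.83 at rho = 0.7.

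**5. Paired t-test, difference SD 10.15 (noncentral t).** Power is 0.848, 0.883 and 0.911 at n = 11, 12 and 13. The z-test at n = 11 gives 0.913.

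**The case against.** Several points can be made for the plan.

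- **One-Factor may mean one-factor repeated measures.** Stage is the single factor, the outcomes are followed over time, and Tukey-Kramer does not by itself fix the error term. This stands as a possible intention. But the SAP does not say it, and an analyst following the text could run either version and get different answers.
- **A sample size of 11 also fits a one-sample test against a fixed reference mean.** The arithmetic is indeed the same. But the power section's own outcome is device versus no prosthesis within a subject, and a fixed-reference test would not address it.
- **The error is only conservative, and 30 may be enrolled.** Both are true. There is no inflation of false positives, and with 30 analysed the loss is small in most scenarios. But the 30 is an estimate that may include intact individuals, section IV.E of the protocol lists a lack of subjects with amputation as a risk, and the SAP's own figure is a minimum of 11.
- **The drop in stated power to 0.85 is not caused by adding a subject term.** Correct: it comes from replacing a known-SD z-test with a t-test. It becomes visible once the actual test is named.
- **The undefined stages may reflect a SAP that is only an excerpt.** That is possible, so this point carries little weight alone.

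**Conclusion.** The concern holds. The outcome and the sizing are within-person, while the named analysis has no subject term and no same-subject test appears anywhere. Of the shortfall at n = 11 and rho = 0.5 with a linear gain, the drop from 0.79 to 0.46 is due to the error term. The remaining gap up to the claimed 0.90 comes from using an omnibus test and from sizing on a z-test with known SD.

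This size rests on the literal reading, compound symmetry, an analysed number near the minimum, and an assumed correlation and gain shape that the SAP does not fix. That the analysis is not specified as within-person is certain; how much power would be lost is not. Because it concerns the primary analysis and is easily repaired, it should be corrected before any data are analysed.

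**What to change.** 1. Make the primary CAPPFUL test a two-sided paired t-test at 0.05 on each subject's change (Point Digit at a named stage minus no prosthesis), reported with a 95% CI. Define stages 0, 1 and 2.
2. For CAPPFUL and WI, replace the One-Factor ANOVAs with a repeated-measures ANOVA or a linear mixed model (stage fixed, subject random). Take multiplicity-adjusted stage contrasts from that model.
3. Give WI the same within-subject paired comparison, since the SAP also calls it primary. How alpha is shared between the two measures is a separate matter that this change does not settle.
4. Restate power at 11 subjects as about 0.85 for the paired t-test, assuming a difference SD of 10.15.

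The cost is SAP wording and a few lines of code, with no new data. The stated power at 11 subjects falls from 0.90 to about 0.85. Keeping 0.90 would need 13 analysed subjects.

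### The one-sample t-test against the Arm Dynamics dataset ignores the dataset's own sampling error, so when populations are compared its Type I error exceeds 0.05 unless the dataset is large

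*SAP*

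**What the plan says.** The SAP, under Data analysis, sets the test for the external comparison: "One-sample t-tests will be used to compare the outcome measures with the existing dataset from Arm Dynamics". It fixes the level for all tests: "A probability of Type I error of 0.05 will be used to determine statistical significance". It adds an optional matched analysis: "Pair-wised t-tests may be performed when a subject matches the demographic, functional, or psychological profiles of an existing subject within the dataset". That sentence shows that the reference is a set of individual people, not a published constant.

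Neither document gives the dataset's size, mean or SD, states the null hypothesis for this comparison, or says that the dataset mean is to be taken as a fixed benchmark.

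Two other parts of the plan do not use the dataset. The Power calculation section defines the primary outcome within subjects: "The primary outcome measure will be the improvement in intra-subject CAPPFUL scores while using the Point Digit system versus no prosthesis". The Data analysis section also compares stages 0, 1 and 2 among the trial's own subjects.

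**The concern.** A one-sample t-test asks whether the trial mean differs from a known number. The mean of a finite set of subjects is not known in that sense; another set of similar subjects would have given a different mean. The test counts the trial's sampling error and omits the dataset's. If the question is whether two populations differ, the standard error is too small and the stated 5% level is not kept.

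The test is applied to the outcome measures, and the Data analysis section names CAPPFUL and WI as primary measures. It is also the main planned comparison with people outside the trial, so a chance difference between the two groups could be reported as a real difference from other prosthesis users.

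**Working it through.** **Inputs**

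- Trial size n = 11, from the SAP, Power calculation: "a sample size of at least 11 subjects will be needed".
- Level 0.05, from the SAP. Sidedness is not stated; two-sided is taken because it reproduces the plan's sample size exactly (step 1).
- Effect for power: 10.15 points, one SD, from the SAP, Power calculation.
- Dataset size m: not given, so a range is shown. The value 17 is the sample in the SAP's source [28]. The SAP does not say that this is the Arm Dynamics dataset.
- Assumptions: normal data, equal variances, no subjects in common.

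**Step 1: the plan's own figure.** For a z-test with known SD and a one-SD difference, n = (1.960 + 1.282)² = 10.51, rounded up to 11. The SAP's figure is reproduced. It belongs to the within-subject comparison and does not depend on the external dataset. (The one-sided version gives 9.)

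**Step 2: the missing term.** The variance of (trial mean − dataset mean) is σ²(1/n + 1/m). The one-sample test uses only σ²/n. Its standard error is too small by sqrt(1 + n/m).

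**Step 3: actual Type I error under equal population means.**

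Type I error = 2 × P(T₁₀ > t₀.₉₇₅,₁₀ / sqrt(1 + 11/m)), with t₀.₉₇₅,₁₀ = 2.228.

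Example at m = 17: sqrt(1 + 11/17) = 1.283; 2.228/1.283 = 1.736; 2 × P(T₁₀ > 1.736) = 0.113.

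| m (assumed) | SE ratio | Formula | Simulation (400,000 runs) |
|---|---|---|---|
| 17 | 1.28 | 11.3% | 0.113 |
| 30 | 1.17 | 8.6% | 0.086 |
| 50 | 1.10 | 7.1% | 0.071 |
| 100 | 1.05 | 6.1% | 0.060 |
| 200 | 1.03 | 5.5% | 0.055 |
| 500 | 1.01 | 5.2% | 0.052 |
| 1000 | 1.01 | 5.1% | 0.051 |

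On these assumptions the error falls below 10% from m = 22, below 7.5% from m = 43 and below 6% from m = 106.

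**Step 4: sensitivity.**

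- *Larger n.* The 11 is a minimum, and the excess grows with n. The Protocol (Description of Population to be Enrolled) says: "An estimated total of 30 subjects will be enrolled". Those 30 may include intact individuals, so using all of them here is only an assumption. With n = 30 the error would be 22.9% at m = 17, 11.7% at m = 50 and 6.6% at m = 200.
- *Unequal SDs.* With n = 11 and a dataset SD of 0.5 or 1.5 times the trial SD, the error is 6.6% or 18.6% at m = 17, and 5.3% or 7.4% at m = 100.

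**Step 5: the two-sample alternative at n = 11.** Simulated Type I error of the Welch test is 0.050 to 0.051 at every m in the table. Power for a one-SD difference:

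| m (assumed) | Welch | Pooled t-test (equal variances) |
|---|---|---|
| 17 | 0.69 | 0.70 |
| 50 | 0.80 | 0.84 |
| 200 | 0.84 | 0.90 |

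A one-sample t-test against a truly fixed mean has power 0.85.

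**The case against.** Four points can be made for the plan.

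- **The size of the error is unknown.** The documents do not give m, and with several hundred subjects the excess is trivial. Nothing ties the figure of 17 to this dataset. This stands: the result is conditional on m, and a material inflation has not been demonstrated. But a reader of the SAP cannot rule one out, and the direction is the same for every finite m.
- **The reference may be meant as fixed.** The null hypothesis of a one-sample t-test is equality to a given value, and on that reading the 5% level is correct under the usual normal assumptions. The reading is legitimate but narrower: it supports a conclusion about one number, not about the population behind the dataset. The SAP does not adopt it, and its description of the comparator as a dataset of subjects points the other way.
- **The comparison is peripheral.** No sample size, power claim or stated hypothesis rests on it. That stands and limits the importance of the point, although the test does cover the primary measures.
- **Confounding may matter more than sampling error.** The comparator is neither concurrent nor randomised, and no choice of t-test changes that. This stands too. It is a reason for cautious interpretation, not for keeping a standard error that is too small.

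**Conclusion.** The concern holds as stated, for the external comparison only. If the null hypothesis is equal population means, the one-sample t-test exceeds its nominal 5% for any finite dataset. At n = 11, with equal variances and independent samples, the error is roughly double the nominal level if the dataset has about 20 subjects, about 7% at 50, and practically nominal at several hundred. These figures shift with the dataset's SD and rise with n, so they show the scale of the problem and are not precise estimates. The plan should be corrected here, but the point does not threaten the primary result. Confidence in its practical importance is moderate, because m is not known.

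**What to change.** 1. State the null hypothesis for this comparison, and the dataset's n, mean and SD for each outcome measure compared.
2. If the aim is to compare populations, replace the one-sample t-test with a two-sample Welch t-test computed from those three figures, and report the difference with a 95% confidence interval.
3. If the dataset mean is meant as a fixed benchmark, say so and limit the conclusion to a difference from that value.
4. Label the optional matched-subject t-tests as exploratory.
5. State that the comparator is non-concurrent and non-randomised, and that Welch does not remove the resulting bias.

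The cost is SAP wording and three summary figures per measure from the dataset holder. With Welch, power for this comparison falls below the 0.85 of the fixed-mean test, by an amount that depends on m (step 5 of the working). That loss is specific to Welch: if equal variances could be justified, a pooled t-test would have about the same power at m = 50 and more at m = 200. The planned sample size of 11 does not change.

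### The one-sample t-tests against the Arm Dynamics dataset name no comparable subset, test condition or adjustment, so a difference in case-mix can pass for a Point Digit effect or hide one

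*SAP*

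**What the plan says.** The SAP, under Data analysis, states: "One-sample t-tests will be used to compare the outcome measures with the existing dataset from Arm Dynamics". This is a firm commitment. The sentence names no subset of records, no test condition and no covariate. It stands in the paragraph on measuring the device's effectiveness "using the primary measures: CAPPFUL and WI", and that paragraph ends by setting the 0.05 significance level.

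Two softer provisions follow. The first is matching: "Pair-wised t-tests may be performed when a subject matches the demographic, functional, or psychological profiles of an existing subject within the dataset". The second is exploration of attributes: "Then, differences can be studied based on the prosthetic components, amputation level, or other subject attributes".

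On the trial side, Protocol IV.B says: "The subject population will consist of a convenient sample of people". Eligibility is wide: "The subjects must be normal intact individuals and/or persons with amputation who are able to understand and follow directions in English". No limit is set on amputation level, digits lost or earlier prosthesis use, and the text of the SAP adds no entry criteria. The source of the reference dataset also collects the trial data: "Data will be gathered by Arm Dynamics and provided to the independent researchers".

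**The concern.** A one-sample t-test asks whether the trial mean differs from a reference value. It can speak about the device only if the people and conditions behind that value are like those in the trial. Here nothing makes them alike. One side is recruited by convenience, and the other is a set of existing records whose size, amputation levels, devices and test conditions are not given.

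Test condition is open as well. The SAP measures CAPPFUL with and without the device and compares results across three stages, but it does not say which trial score is set against which kind of dataset score.

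At stake is the meaning of a p-value below 0.05 from this comparison. It could reflect milder amputations, other components or another test condition. Equally, a more severely affected trial group could conceal a benefit.

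**Working it through.** **Inputs**
- From the SAP, Power calculation: SD 10.15, taken from 17 published partial hand amputees; difference of interest 10.15; power 0.9; Type I error 0.05; stated minimum n = 11.
- From Protocol IV.B: "An estimated total of 30 subjects will be enrolled".
- Assumed, because the documents do not give them: the case-mix gap, the number of dataset records, a two-sided test, and that the SD of 10.15 applies to both groups.

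**The plan's own figure**

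Two-sided one-sample z-test: n = ((1.960 + 1.282) × 10.15 / 10.15)² = 10.51, rounded up to 11. The stated figure reproduces, and this point does not dispute it.

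**Gap at which the external test becomes significant**

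With n = 11, t(0.975, 10 df) = 2.228. The standard error is 10.15 / √11 = 3.06, so the observed gap needed is 2.228 × 3.06 = 6.82 CAPPFUL points.

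**Chance of significance with no device effect**

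If case-mix alone shifts the trial mean by d SD, the test statistic follows a noncentral t distribution with noncentrality d√n and n − 1 degrees of freedom. For example, at n = 11 and d = 0.5 the noncentrality is 0.5 × 3.317 = 1.66.

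| Assumed gap | Points | n = 11 | n = 30 |
|---|---|---|---|
| 0 | 0 | 5% | 5% |
| 0.25 SD | 2.5 | 12% | 26% |
| 0.5 SD | 5.1 | 32% | 75% |
| 1 SD | 10.15 | 85% | over 99% |

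More subjects do not help: a fixed bias is detected more often as n grows.

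**A second, separate error that bears on the remedy**

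The one-sample test treats the reference mean as a known constant. If it is estimated from m records, the true standard error of the difference is 10.15 × √(1/n + 1/m), larger than the one used by a factor √(1 + n/m). At n = 11, with identical populations, simulation gives a Type I error of about 0.11 for m = 17, 0.07 for m = 50 and 0.06 for m = 100. Narrowing the reference set while keeping a one-sample test would therefore exchange part of one error for another.

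**The case against.** The strongest reply is that the SAP does attend to case-mix. It foresees pairing subjects with similar dataset subjects and looking at differences by component and amputation level. That is true and should be credited, so a reader who infers that the SAP overlooks these factors goes too far. But both steps are permissive, no rule says what counts as a match, and neither restricts or adjusts the one-sample test.

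A second reply is that the external comparison is not the main evidence. This stands. The primary outcome in the SAP's Power calculation is each subject's own change in CAPPFUL between no prosthesis and the device, and the stated hypothesis concerns the rise from stage 0 to stage 2. Neither draws on the dataset.

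Third, the size of the problem is assumed. This also stands: any t-test rejects more often when means differ, and the figures do not show that a gap exists. It could run in either direction.

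Fourth, the SAP never says that every record will be used. It is silent on the subset, and it relies on terms that its text does not explain (the stages, the two systems), so the dataset may be described elsewhere. The recruited group may also prove narrower than the protocol allows, since the power calculation refers to partial hand amputees. None of this puts a restriction into the analysis plan.

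A reader might also infer, because Arm Dynamics supplies both sides, that trial subjects appear in the dataset and that this invalidates the tests. The documents do not support that. Overlap is possible but not shown. A paired t-test allows correlation within pairs, and a trial subject's record inside the reference mean would tend to dilute a difference rather than create one. Removing such records is simple good practice.

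**Conclusion.** The concern holds for the external comparison only. As written, the SAP commits to an unadjusted test of a convenience sample against a dataset for which it specifies no comparable subset or test condition, and judges it at 0.05. A significant result could not be attributed to the Point Digit, and a null result could not rule out a benefit. Under the power calculation's n and SD, modest assumed gaps of 0.25 to 0.5 SD raise the chance of a spurious finding from 5% to between 12% and 32%, and at the protocol's 30 subjects to between 26% and 75%. These figures illustrate sensitivity; they do not estimate the actual bias. The sample size, the within-subject primary outcome and the comparison across stages are untouched by this point. It should be corrected, but it does not undermine the trial's main contrast.

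**What to change.** Amend the SAP's Data analysis section before any trial scores are seen:

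1. Define the comparator as dataset records from adults with partial-hand loss, tested in the same condition as the trial score being compared, and within the amputation patterns enrolled.
2. Remove any record that belongs to a trial subject.
3. Replace the one-sample test with a two-sample Welch comparison, or with a regression adjusted for amputation level where numbers allow, so that the reference set's sampling error is carried.
4. Report the difference with a confidence interval and label it supportive.

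The cost is SAP wording, a data filter, and some precision. With n = 11 and a common SD of 10.15, the standard error of the difference is 10.15 × √(1/11 + 1/50) = 3.38 points for an assumed 50 retained records and 10.15 × √(1/11 + 1/17) = 3.93 for an assumed 17, against the 3.06 that the one-sample test would use. The wider interval is the honest one. With about 11 trial subjects some amputation levels may be empty, so the SAP should name the unadjusted Welch comparison as the fallback.
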